## **Introduction**

Depression is one of the most serious mental diseases, bringing great burden to society and families. Currently, antidepressant drugs commonly used in clinic mainly are tricyclic and monoamine substance reuptake inhibitors discovered in the 1950s and 1960s, which are classic monoamine strategy drugs. They improve depressive symptoms by increasing the concentration of monoamine transmitter in the brain, but their onset time is slow and efficacy is low. These drugs are only effective for about 60 - 70% of patients with depression, while the remaining 30% may be patients with treatment-resistant depression. In addition, the onset time is delayed and often takes weeks and months to begin. Some even cause side effects of drugs (such as anxiety) before taking effect, aggravating the suicidal tendency of depressive patients. In recent years, ketamine, as a new antidepressant, has been hailed as the largest discovery in the past half century because of its rapid antidepressant effect (rapid improvement of mood in a few hours) and its efficacy in over 70% of patients with refractory depression. However, ketamine is classified as a psychotropic drug due to its potential addiction, which limits its application in clinical anti-depression treatment.

[name]'s research group applied a variety of research tools of neuroscience, such as behavioral pharmacology, electrophysiology and photogenetics, to elucidate the neurological mechanism of ketamine's rapid antidepressant effect, that was, ketamine blockaded the N-methyl-D-aspartate receptor (NMDAR) and low-voltage-sensitive calcium channel (T-VSCCs)-dependent cluster discharges in the lateral habenular nucleus located in the reward center, which led excessive inhibition of downstream monoamine reward brain regions, and ultimately caused rapid antidepressant effects.

At the same time, animal experiments had also confirmed that cluster discharges in the lateral habenular nucleus mediated the occurrence of depression, and the cluster discharges were dependent on NMDA receptors and T-VSCC. In vitro brain slice, electrophysiological studies showed that Mibefradil (10 $\mu$ m), a T-VSCCs inhibitor, could significantly inhibit the spontaneous cluster discharges of lateral habenular nucleus neurons and cluster discharges induced by hyperpolarization. Meanwhile, Mibefradil (10 nmol, 1  $\mu$ l, each side) was injected bilaterally into the lateral habenular nucleus to inhibit T-VSCCs-mediated cluster discharges in neurons, sufficiently producing antidepressant effects. This series of studies provides a new idea for the rapid development of antidepressant drugs, that is, inhibiting T-VSCCs to achieve rapid antidepressant.

Ethosuximide is a T-VSCCs inhibitor. The IC50 of T-VSCCs current suppression is 0.3-1 mM, and the IC50 of sodium channel current suppression on squid axon is 60 mM. Therefore, it has higher selectivity to T-VSCCs. Ethosuximide can enter cerebrospinal fluid through the blood-brain barrier, inhibit T-VSCCs on the lateral habenular nucleus neurons, and then inhibit the cluster discharge of neurons, resulting in a rapid antidepressant effect.

The antidepressant effect of ethosuximide has been confirmed in animal experiments. It showed significant antidepressant effects in chronic restraint stress(CRS)-induced depression mice, acute congenitally learned helpless(cLH) rats and epileptic seizures model animals with depressive symptoms(WAG/Rij rats). In the CRS-induced depression mice model, the behavioral despair phenotype of the depression mice was significantly improved after a single intraperitoneal injection of ethosuximide (200 mg/kg) for 1 hour, which showed that the immobility time in forced swimming was significantly reduced. Meanwhile, the pleasure-deficiency behavior of mice was also significantly improved, showing a significant increase in preference for sugar. In learned helpless congenital depression rats, the immobility time of congenital depression rats in forced swimming was significantly reduced after a single intraperitoneal injection of ethosuximide (200 mg/kg) for 1 hour (unpublished data). In the model animals of epilepsy seizures with depressive symptoms (WAG/Rij

rats), 300 mg/kg ethosuximide was given daily through drinking water for 17 consecutive days at the age of 5 months with obvious epileptic seizures, which resulted in significant antidepressant effect (the immobility time of forced swimming was significantly reduced).

In conclusion, ethosuximide can inhibit the T-VSCCs on the lateral habenular nucleus neurons and then inhibit the cluster discharges of neurons, resulting in a rapid antidepressant effect. The purpose of this study was to explore the antidepressant efficacy of ethosuximide tablets in patients with refractory depressive disorders, to preliminarily evaluate the clinical efficacy and safety, and to explore the possible mechanism of its antidepressant effect.

#### **Research Purpose**

To evaluate the clinical efficacy and safety of ethosuximide in patients with treatment-resistant depression, and to explore its underlying mechanism.

## **Research Contents**

### **Subject selection criteria**

#### **Diagnostic criteria**

Diagnosis of major depressive disorder(single or recurrent episodes) is made according to The fifth Edition of Diagnostic and Statistical Manual of Mental Disorders(DSM-V )criteria. All patients with previous or current episodes are ineffective after treatment with two different recommended doses of antidepressants for a full course of treatment (maximum treatment dose of at least 6 weeks).

#### **Inclusion criteria**

1. Inpatient of both sexes are aged from 18 to 65 years;
2. Diagnosis of major depressive disorder(single or recurrent episodes) is made according to DSM-V criteria;
3. Subjects with previous or current depressive episodes did not response to two different antidepressants with recommended doses and adequate duration (maximum treatment dose of at least 6 weeks);
4. The subjects who will score more than or equal to 22 points on the MADRS scale at screening and baseline period;
5. The subjects who will score more than or equal to 3 points on the first clause of MADRS scale at screening and baseline period;
6. Subjects who will sign written informed consent and volunteer to participate in the clinical study.

#### **Exclusion criteria**

1. Diagnoses of other mental disorders (such as organic mental disorders, schizophrenia, bipolar and related disorders, anxiety disorders, obsessive-compulsive disorders and so on) are made according to DSM-V criteria;
2. Depressive episodes, such as depression caused by hypothyroidism, secondary to a systemic disease or an organic mental disorder caused by a neurological disease;

3. Subjects with a history of attempted suicide, or currently at high suicide risk, or with suicide behavior/attempt, or scoring more than or equal to 3 points on the 10th clause of MADRS scale;
4. Subject whose score of MADRS scale in baseline period will be 25% lower than that in screening period;
5. Subjects with a history of severe or poorly controlled cardiovascular, liver, kidney, blood, endocrine, respiratory diseases, etc;
6. Subjects with a history of epileptic seizures, except for a single febrile convulsion in children;
7. Researchers believe that the results of subjects' physical and laboratory examinations are clinically significant abnormalities in screening or baseline period. The following indicators exceed the following criteria: 1)ALT or AST levels are 1.5 times higher than the upper limit of laboratory normal values. 2)Thyroid Function are 1.1 times higher than the upper or lower limit of normal values. 3) Serum creatinine values are 1.1 times higher than the upper limit of normal values. 4)The levels of blood urea nitrogen are higher than the upper limit of normal values;
8. The result of electrocardiogram (ECG) is abnormal in screening or baseline period, such as male subjects with QTc interval ( $> 450$  ms) and female subjects with QTc interval ( $> 470$  ms) , and the researchers thought it is not suitable for selection;
9. Subjects could not swallow oral medicines or have a history of gastrointestinal surgery or any other diseases that may interfere with drug absorption, distribution, metabolism or excretion;
10. Monoamine oxidase inhibitors (MAOIs) are taken by subjects now or within 2 weeks before screening. Subjects who took antipsychotics, antidepressants or mood stabilizers before randomization and these drugs' cleaning phase had less than five half-lives. Subjects who took fluoxetine within 1 month before screening. Subjects who continue to take Chinese medicines with antidepressant effects specified in the instructions after signing informed consent.

11. Subjects who received modified electroconvulsive therapy (MECT) , transcranial magnetic stimulation (TMS), vagal nerve stimulation (VNS), or systematic psychotherapy within 3 months before screening;
12. Subjects with a history of allergies to two or more foods or drugs;
13. Subjects who addicted to alcohol or substances within 6 months before screening;
14. Prenatal, lactating, or reproductive women who had positive results of HCG tests before participating in the study; Male and female subjects will not take effective contraceptive measures or plan to be pregnant within 3 months after the study;
15. Subjects who participated in clinical research within 30 days before signing the informed consent form for this study;
16. According to the judgement of the researchers, other situations are not suitable for clinical research.

#### **Withdrawal criteria**

Subjects withdrawing from the study: subjects who quit voluntarily and who need to withdraw after medical assessment of researchers.

1. Subjects who break off informed consents at any time;
2. Subjects who are lost to follow-up;
3. Severe adverse events, or intolerable adverse events happen, and are identified by the researchers that subjects need to quit;
4. Subjects who violate the protocol severely that affect the assessment of safety and efficacy of the research definitely;
5. Subjects who get psychiatric symptoms, mania, suicidal or self-injurious behaviors during the study;
6. Subjects who are pregnant during the study;
7. Subjects need to withdraw from the study in other situations after assessment of researchers.

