#### **Treatment Period (Day 42±1) - Visit 10**

Visit will be conducted on day42±1 after randomization.

Contents of visit:

1. Scale score: MADRS、 QIDS-SR、 HAMA、 YMRS;
2. Laboratory tests:  
blood concentration of ethambutamine.

complete blood count: hemoglobin (HGB), red blood cell count (RBC), white blood cell count (WBC), neutrophil count (NEUT), lymphocyte count (LY), platelet count (PLT);

routine urine: PH, white blood cells, erythrocyte (ERY), nitrite (NIT), protein, glucose (GLU), ketone body (KET), urinary cholanogen (UBG), bilirubin;

blood biochemical examination: aspartate aminotransferase (AST), glutamate aminotransferase, alkaline phosphatase (ALP), glutamyl transpeptidase (GGT), lactate dehydrogenase (LD), total protein, albumin (ALB), urea nitrogen (BUN), creatinine, creatine kinase (CK), total bilirubin (TBIL), direct bilirubin (DBIL), uric acid, blood sugar (Glu), triglyceride (TG), total cholesterol (TC), high density lipoprotein (HDL), low density lipoprotein (LDL), sodium (Na), potassium (K), chlorine, phosphorus (P), calcium (Ca), prolactin (PRL);

3. ECG: 12 leads cardiogram;
4. Vital signs: including blood pressure (sitting position), heart rate, respiratory rate, body temperature and weight;
5. Records of adverse events;
6. Records of combined medication.

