## Flow chart of experiment

## Dealing with Adverse Event

In the study, doctors will monitor the side effects of drugs. If subjects have side effects, the doctor will treat them accordingly. If the subjects could not tolerate side effects, they will be stopped to take research drugs and withdraw from the study.

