5.1 General Principles

The analysis will be performed after data collection is completed. Statisticians and relevant researchers of the study group will use the latest version of SPSS statistics for data analysis, and all data analysts are blinded to treatment allocation.

The research data are mainly analysed on the basis of intention-to-treat (ITT) principle. All randomized participants are analysed according to the intervention to which they are randomized initially in the ITT analysis. The per-protocol (PP) analysis is another analysis method. In the per-protocol (PP) analysis, participants who do not receive treatment or do not provide any follow-up data should be excluded and grouped to analyse according to the intervention they actually received.

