5.2 Handling of Missing data

Unless otherwise specified, missing values will not be imputed.

[figure not shown]

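### The Protocol ties stopping drug for harm, and severe protocol violation, to leaving the study and schedules no MADRS afterwards, so the SAP's ITT analysis is not supported by its data or method

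*Protocol*

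**What the plan says.** The Protocol's Withdrawal criteria open by defining withdrawal as leaving the study: "Subjects withdrawing from the study: subjects who quit voluntarily and who need to withdraw after medical assessment of researchers". Three of the listed reasons matter here:

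- adverse events: "Severe adverse events, or intolerable adverse events happen, and are identified by the researchers that subjects need to quit";
- protocol violation: "Subjects who violate the protocol severely that affect the assessment of safety and efficacy of the research definitely";
- psychiatric events: "Subjects who get psychiatric symptoms, mania, suicidal or self-injurious behaviors during the study".

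Under Dealing with Adverse Event, the Protocol says of subjects who cannot tolerate side effects that "they will be stopped to take research drugs and withdraw from the study". Neither section has a category for a patient who stops drug but continues to be assessed. The visit sections run from screening to Visit 10 ("Visit will be conducted on day42±1 after randomization"), and none is an early-termination or post-withdrawal visit.

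SAP 5.1 makes ITT the main principle: "All randomized participants are analysed according to the intervention to which they are randomized initially in the ITT analysis". SAP 4.1 limits the efficacy analysis to patients who took study drug and have at least one later scale score. SAP 5.2 states: "Unless otherwise specified, missing values will not be imputed". SAP 5.4 compares the arms by two-way repeated-measures ANOVA.

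**The concern.** An ITT comparison needs outcomes on patients whether or not they finish treatment. Here the events most likely to stop treatment also end the schedule of assessments. Those events are close to the outcomes. Mania is what the YMRS, a secondary measure, is there to record. Suicidality is what the tenth MADRS item addresses in exclusion criterion 3, and individual MADRS items are secondary measures. Both scales may stop at the event they should capture.

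The arms differ only in the first two weeks, with the dose raised over Days 1 to 5, so unequal intolerance is plausible. If the two arms lose different kinds or numbers of patients, the comparison of those who remain is no longer the randomised comparison.

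Safety data are affected too. After dosing starts, the safety laboratory panel and ECG are scheduled only at Day 14 and Day 42. A patient withdrawn for harm before Day 14 has neither on schedule.

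**Working it through.** **Inputs from the documents.** There are 20 patients per arm (Protocol, Number of subjects; SAP 2.2), and nine post-baseline MADRS visits: Days 2, 3, 4, 6, 10, 14, 22, 29 and 42. No alpha, power, effect size, SD or expected withdrawal rate is given, so the only figure to reproduce is 20 + 20 = 40. The main check is textual.

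**Step 1: what the ITT statement needs, and what the plan supplies.**

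- *Everyone randomised.* SAP 4.1 admits only dosed patients with a post-dose score. This conflicts with SAP 5.1 whatever the withdrawal rule.
- *Scores after treatment stops.* None is scheduled for the withdrawal reasons above.
- *A method that tolerates gaps.* SAP 5.4 describes sums of squares, mean squares, F values and corrected within-group degrees of freedom. That is the classical ANOVA, which needs a score at every time point. SAP 5.2 fills no gaps.

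**Step 2: follow one patient.** Suppose drug is stopped for intolerance just after the Day 6 visit. Scores exist at Days 2, 3, 4 and 6 (4 of 9). Days 10, 14, 22, 29 and 42 (5 of 9) are missing. The patient is in the Efficacy Set, but the classical ANOVA excludes the patient, so the four scores already taken are lost as well.

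**Step 3: size of the bias (all inputs assumed).** Let w be the share of an arm that is withdrawn, and s the number of MADRS points by which those patients improve less than completers. Then:

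- full-arm mean improvement = completer mean − w × s, so dropping them overstates the arm by w × s;
- bias in the difference between arms = w₁s₁ − w₂s₂, which equals (w₁ − w₂) × s if s is the same in both arms.

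With a gap of 10 to 20 percentage points (0.10 × 20 = 2 to 0.20 × 20 = 4 more patients lost in one arm) and s of 5 to 10 points:

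- 0.10 × 5 = 0.5
- 0.10 × 10 = 1.0
- 0.20 × 5 = 1.0
- 0.20 × 10 = 2.0

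The bias is 0.5 to 2.0 points in favour of the arm that loses more patients. It is zero if the arms lose equal shares with equal s, and it changes sign if those leaving had improved more than completers.

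**Step 4: loss of numbers (assumed rates).** At 10% withdrawal, 20 × 0.90 = 18 complete cases per arm remain; at 20%, 20 × 0.80 = 16. For an assumed standardised difference of 0.8 and two-sided alpha of 0.05, normal-approximation power falls from 72% (20 per arm) to 67% (18) and 62% (16). These rates cover every cause of loss, including withdrawal of consent and loss to follow-up, which no rule can prevent.

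**The case against.** The strongest reply is that several sharper readings go beyond the text.

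- *That later scores are never collected.* The documents do not forbid it; they are silent. The Protocol's flow chart and the consent pages were not available for this check, and either might provide for an early-termination assessment. What stands is that the written visit list has none.
- *That an ITT analysis is impossible, or that no analysis could repair the loss.* Scores before withdrawal exist from Day 2. A likelihood-based model can analyse them by randomised arm if data are missing at random. This stands. But that assumption is weak when removal follows suicidality or mania, and the SAP does not plan such a model.
- *That anyone who stops drug or breaks the protocol is removed.* The text is narrower: violations must be severe and affect assessment, adverse events need the researchers' judgement, and the explicit link between stopping drug and leaving concerns intolerable side effects.
- *That the bias must favour the arm losing more patients.* A patient with intolerable side effects may have improved on MADRS, and a manic patient may score low.
- *That follow-up for harm ends.* The Protocol says side effects will be treated, and SAP 5.5.1 summarises events leading to discontinuation or death. How long follow-up lasts is not stated.

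A further reply is that scores taken after another treatment starts answer a treatment-policy question, which a small preliminary study need not ask. But the SAP itself chose ITT as its main principle. Scores that are collected can be set aside for another question; scores that are not collected cannot be recovered.

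**Conclusion.** The point holds as a mismatch between documents. The Protocol's withdrawal rules, read with its visit list, end scheduled assessment for reasons related to outcome. The SAP's lack of imputation, its complete-case ANOVA and its narrower Efficacy Set then leave the stated ITT analysis unsupported. The withdrawal rule is one cause among these, not the only one.

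The illustrative bias of 0.5 to 2.0 MADRS points rests wholly on an assumed withdrawal gap and an assumed shortfall equal in both arms; nothing in the documents sets either. A reader might infer that the trial cannot yield an ITT result or that its bias has a known sign. The documents support neither. The plan should be changed, because the remedy uses visits that already exist and each lost patient is 1/20 = 5% of an arm.

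**What to change.** Leave the rules on when drug stops as they are. Change data collection and analysis only:

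1. In Withdrawal criteria and Dealing with Adverse Event, separate stopping study drug from leaving the study.
2. State that patients who stop drug or severely violate the protocol are asked to attend all remaining scheduled MADRS and safety visits unless they withdraw consent. A few landmark visits would not be enough for the present analysis: a patient who stops on Day 4 and returns only on Days 14 and 42 still lacks Days 6, 10, 22 and 29.
3. Remove severe protocol violation as a reason to end follow-up.
4. Flag scores taken on other treatment.
5. In SAP 5.4, replace the complete-case ANOVA with a likelihood-based repeated-measures model that uses all available scores as randomised. Add a sensitivity analysis for data missing not at random.
6. Reconcile the Efficacy Set in SAP 4.1 with the ITT statement in SAP 5.1.

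The cost is a protocol amendment, a sentence in the consent form and the SAP edits. No new visit dates are needed. The drawback is that some later scores will reflect other treatment, hence the flag.

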#### **Suspension criteria**

Research suspension means that clinical research has not been completed according to the plan, and has been stopped halfway. The main purpose of research suspension is to protect the rights and interests of subjects, ensure the quality of research and avoid unnecessary economic losses.

1. If serious security problems happen, the study will be stopped in time.
2. If we find the drugs have no clinical value, the study will be discontinued to avoid delaying treatment of the subjects and unnecessarily economic losses.
3. If we find that the clinical study has major errors which make us difficult to evaluate drug effects, or a well-designed study, which has significant deviations in the implementation process, is difficult to evaluate drug effects for us, it will be discontinued.

#### **Prohibited drug and prohibited treatment**

Prohibited drug:

1. Antipsychotics, antidepressants, mood stabilizers, antianxiety drugs, central stimulants and any other psychotropic drugs (except those permitted for combination);
2. Chinese medicines with antidepressant effects specified in the instructions.

Prohibited treatment:

1. Antipsychotics, antidepressants, mood stabilizers, antianxiety drugs, central stimulants and any other psychotropic drugs (except those permitted for combination).
2. Chinese medicines with antidepressant effects specified in the instructions.

#### **Combined medication and treatment**

1. In the study, zolpidem, zopiclone, Eszopiclone and zaleplone are allowed to be combined for the treatment of insomnia and taken before retiring. The dosage should not exceed the upper limit specified in the instructions, and the cumulative use time of the study period after randomization should not exceed one week.
2. Drugs for the treatment of original somatic diseases are permitted to take. But the types and doses of drugs should be kept as constant as possible in the study.

## **Research protocol**

### **Research medication**

1. Ethosuximide, Drug specification: 250mg/capsule, Pfizer Inc.
2. Escitalopram, Drug specification: 10mg/pill, Xian Janssen Pharmaceutical Ltd.

